 - Upon arrival to the room, members of the designated IHCA team and other care providers will be informed via a posted sign that the event is a videorecorded research simulation. They will then begin participate in the simulation at their discretion.
 - We will adapt existing, tested cardiac arrest simulation scenarios for use in this study. While the provided case histories will describe patients of different ages, genders, and presenting complaints, all scenarios will feature cardiac rhythms demanding substantively identical resuscitative actions (Figure 1).
 - The telemedical link (or a control video) will be activated by the research coordinator after the arrival of the team lead or after five minutes have elapsed, whichever occurs first. At this time, the coordinator will also provide simple, brief, and scripted "just-in-

time” training to the mobile telemedicine cart and, for intervention events, the telemedical intensivist copilot.

- For mock codes randomized to intervention, critical care physicians with experience in telecritical care who consent to participate in this study will provide standardized consultation to the on-site team. These IHCA team “copilots” will advice and assistance to the on-site team leader including help with ensuring high-quality, minimally-interrupted chest compressions and prompt defibrillation, assisting situational awareness, encouraging etiologic evaluation, and promoting leadership behaviors.
- The event will be terminated when team performs an action that was pre-determined for the scenario to result in return of spontaneous circulation. The simulation will be terminated no later than 25 minutes after initiation if team fails to perform this pre-determined action. Most simulations are expected to last 10-12 minutes.
- After simulation termination, participants will complete a brief, anonymous questionnaire.
- Local code team leadership and/or the on-site code team leader will lead a debrief of the event. As needed, the research coordinator or simulation specialist will facilitate discussion of the simulation.
- In progress mock code simulations may be terminated by on-duty hospital clinical leadership or physician code team members if clinical care of patients requires.

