- Mock codes terminated in progress due to competing clinical priorities prior to simulated return of spontaneous circulation will be excluded from the final analysis. If this occurs, the simulation event may be rescheduled at the same hospital for a later date, with the rescheduled mock code assigned to the same study arm as the aborted mock code.
- If systematic problems interfering with study implementation, data collection, or interpretation are identified after study initiation, the study may be halted temporarily while the systematic issues are addressed. Affected events where data is invalid will be considered part of a roll-in phase of the study and will be excluded from data analysis. For each assigned to roll-in event status, we will schedule a make-up event at the affected hospital. Make-up events will be assigned to the same study arm as the roll-in event being replaced and will be interposed randomly with other events at the affected study site.
- Data collection: A research coordinator will be present at all mock codes. Besides study implementation duties, the coordinator will record team composition and function, processes of care, and leadership behaviors. Additional data will be obtained from (1) the simulator device, (2) the defibrillator device, (3) videotaped recording obtained via the mobile telemedicine carts, and (4) a brief questionnaire completed by IHCA team members upon completion of the mock code.
- The primary outcome for the study will be the fraction of time between activation of the telemedicine cart and beginning of the pulse check following the subsequent second full cycle of CPR that the IHCA team does not deliver chest compressions (“no-flow fraction”). Secondary outcomes are shown in Table 1.
 - On-site IHCA team members will complete a brief questionnaire (attached) to measure the subjective experience of individual and team function and — when applicable,

[figure not shown]

Figure 1. Unified structure for mock code scenarios. (ROSC: return of spontaneous circulation.)

opinions about the simulated mock code. Some on-site study participants will also complete a short-form version of the State-Trait Anxiety Index (STAI)¹⁶ validated for measurement of state anxiety (i.e. anxiety/stress at the time the questions are answered).¹⁷ Some participants may complete the survey online using REDCap, a secure web application for building and managing online surveys and databases.¹⁸

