- Off-site IHCA team copilots will complete a brief questionnaire (attached). Most participants may complete the survey online using a version of this questionnaire implemented in REDCap.¹⁸ Opinions about the procedure will also be elicited through post-study qualitative interviews.
- ACLS protocol adherence and violations using a checklist adapted from previously validated research tools.^{8,40}
- Leadership behaviors will be evaluated according to a previously published taxonomy.¹⁹
- Overall function of the IHCA team will also be evaluated using a previously validated instrument.^{20,21}
- Number of simulation events and power analysis: Assuming a baseline no-flow percentage of 0.285,^{10,22} a best-case no-flow fraction of 0.08 (protocol guidelines advise a single 10 second pause in chest compressions for a pulse and cardiac rhythm check every two minutes), and equipment malfunction or simulation termination precluding event analysis for 15% of mock codes, we will require 76 completed mock codes (38 in each arm) to achieve 80% power to detect a 31% relative decrease (9% absolute decrease) in the mean no-flow fraction.
- Study duration: The 76 planned mock codes will be divided between the 7-8 participating institutions. We expect to complete 2-6 simulations at each participating hospital every 2 months. Accounting for scheduling conflicts and expected intermissions during implementation of a new electronic medical record at some study hospitals, we expect study completion to require 18-24 months (and potentially up to 48 months) after simulations begin.

Informed consent (“copilot” physicians): Members of the research team will approach the eligible subjects by email (see attached) or in person at their workplace. Interested subjects will be consented by research team member(s) according to the Intermountain Healthcare Informed Consent Policy.

Table 1: Descriptive & outcome measures for randomized trial of telemedical intensivist IHCA team copilot

Variable	Data source	
	Primary	Secondary
Response team characteristics		
Response team structure	In-person observation	Video recording
Past experience of code team members	Questionnaire	
Primary outcome		
Fraction of pulseless time with no chest compressions*	Simulator mannequin	
Secondary outcomes		
Time from onset of shockable rhythm to defibrillation	Simulator mannequin	Defibrillator
Fraction of chest compressions in target depth range^{23*}	Simulator mannequin	Defibrillator

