Between-group comparisons for continuous variables will employ two-sided t-tests with unequal variance. Comparisons for binary or categorical variables will employ Fisher's exact test or chi-squared test as appropriate. Given clustering within simulations, between-group comparisons of survey responses will employ multilevel logistic (for binary variables) or linear (for continuous variables) regression with a random effect for simulation event. Comparisons of Likert-style variables will use the rank-sum method described Datta/Satten.²⁸

Sample size/power analysis: Assuming a baseline no-flow percentage of 0.285, a best-case no-flow fraction of 0.08 (protocol guidelines advise a single 10 second pause in chest compressions for a pulse and cardiac rhythm check every two minutes), and equipment malfunction or simulation termination precluding event analysis for 15% of mock codes, we will require 76 mock codes (38 in each arm) to achieve 80% power to detect a 31% relative decrease (9% absolute decrease) in the mean no-flow fraction. We therefore expect to enroll 1900 on-site IHCA team members as study subjects (although some participants may participate in >1 mock code).

Waiver of Informed Consent and HIPAA Authorization (for on-site IHCA team members):

We are requesting a waiver of informed consent and HIPAA authorization for on-site IHCA team study participants of this study. Participation in this study is similar to standard training for IHCA team members and involves no more than minimal risk to the subject. Individuals will be notified by means of a prominently displayed poster(s) that a simulation-based research project with video recording is in progress. Such notification will address individuals reasonable expectation of privacy. We will not use video recordings for any purposes except research, and digital video recordings will be stored securely and then transferred to a secure, approved server of the Intermountain network. We will not systematically collect individually identifiable information. The research therefore involves no more than minimal risk to the subjects; the only potential risk is a breach of confidentiality, and protections are in place to safeguard the data. Because risk is minimal, the waiver of consent and authorization will not adversely affect the rights or welfare of subjects.

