Safeguards will be in place to protect subject identity. The data will be protected from improper use or disclosure. The study data will be kept on encrypted, password-protected computers. The data will only be accessible to members of the research team, and all members of the research team with access to identifiable data have completed Human Subjects Protections training and understand the importance of protecting subject privacy and confidentiality. These computers are Intermountain Healthcare devices, which are routinely used for storage of patient data and research data including subject identifiers. No individual subject data will be presented in any presentation, publication, or report related to this research. Data will be presented only in aggregate or as results of statistical analyses and will not include any individual-level data that could be traced to a particular subject.

Risks: Both the off-site copilot and on-site study participants may find participation in simulated IHCA events stressful. This expected stress related to the simulation is similar to the stress participants would experience during performance of their routine job duties or routine training related to these duties. On-site participants will have an opportunity to discuss their experience during the simulation during post-event debriefings.

The only other risk involved with this study is a potential breach of confidentiality. There is a minimal risk of a privacy and confidentiality breach. However, this risk is low given the secured databases and computers that will be employed for data storage.

Benefits: It is unlikely that there will be any direct benefit to you as a result of participating in this study. Participation in simulated IHCA events may improve the skills used by both on-site IHCA team members and the telemedical copilot when managing actual patients suffering medical emergencies. Improved understanding of cardiac arrest resuscitation could improve outcomes for all patients suffering IHCA.

Compensation:

- On-site IHCA team member: A small snack/drink or similar token of appreciation, valued at \$1-2 each, will be available for members of on-site code team after simulation completes
- Telemedical physician copilot: Fleece jacket, valued at approximately \$35-50

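### The primary t-test has no term for hospital or event order; a prespecified model with both is a cheap gain and protects against uneven same-arm replacement

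*Combined protocol and SAP*

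**What the plan says.** The analysis rule for every continuous event-level outcome, including the primary, is one sentence under Data analysis: "Between-group comparisons for continuous variables will employ two-sided t-tests with unequal variance". A random effect is planned only for survey responses. Nothing adjusts for hospital, calendar time or the order of events.

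The design facts that bear on this are:

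- **Allocation** (Randomization): events are randomised in blocks within hospital. The block size is not given.
- **Repetition** (Procedures; Study duration): 76 events are divided among 7 to 8 hospitals. Case histories differ, but "all scenarios will feature cardiac rhythms demanding substantively identical resuscitative actions". Each event ends with a debrief.
- **Overlap of staff** (Sample size/power analysis): 1900 on-site participants are expected, "although some participants may participate in >1 mock code".
- **Replacement** (Procedures): an event stopped for clinical reasons is excluded and may be rerun later at the same hospital, "with the rescheduled mock code assigned to the same study arm as the aborted mock code". Events reclassified as roll-in are also made up in the same arm, at a random place among that site's other events.
- **Power** (Sample size/power analysis): "we will require 76 mock codes (38 in each arm) to achieve 80% power to detect a 31% relative decrease (9% absolute decrease"), allowing for 15% of events being unusable. Neither an SD nor alpha is stated.

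**The concern.** Repeating the same task at the same hospital, with a debrief each time, makes a downward drift in no-flow fraction plausible. An unadjusted t-test treats such a drift as noise, and also ignores the factor used for blocking.

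Replacement raises a second issue. A replacement keeps its arm but can only happen after the event it replaces, at a hospital that has by then started at least one more mock code. If one arm needs more replacements, its analysed events sit later in the sequence on average. The copilot arm depends on a live two-way link and a remote physician, whereas control plays a recording, so uneven replacement is conceivable. Part of any practice effect would then be credited to the copilot.

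**Working it through.** **The plan's own figure.** With two-sided alpha 0.05 (assumed), 80% power and a difference of 0.09, the implied SD is 0.09 × √(n/2) / (1.960 + 0.842).

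- If 38 per arm are analysed: 0.09 × 4.359 / 2.802 = 0.140.
- If 76 already includes the 15% loss, about 32 per arm are analysed (64/0.85 ≈ 76): 0.09 × 4 / 2.802 = 0.128.

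The documents do not settle which applies, so 76 cannot be reproduced from stated inputs alone. I use 38 per arm.

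**Events per hospital.** 76/8 = 9.5 and 76/7 = 10.9, so about 10.

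**Power forgone.** Assume no-flow falls linearly by L from a hospital's first to last event. The trend's variance is L²/12. Removing it from a total SD of 0.140 gives these results (normal approximation, before paying for the extra parameters):

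| L | share of variance, (L²/12)/0.140² | power unadjusted | power with order removed |
|---|---|---|---|
| 0.03 | 0.4% | 80.0% | 80.2% |
| 0.06 | 1.5% | 80.0% | 80.6% |
| 0.09 | 3.4% | 80.0% | 81.4% |
| 0.12 | 6.1% | 80.0% | 82.4% |

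At L = 0.15 the share is 0.001875/0.0196 = 9.6%, the reduced SD is 0.140 × √0.904 = 0.133, and power is Φ(0.09/(0.133 × √(2/38)) − 1.96) ≈ 84%. A simulation at L = 0.15 (8 hospitals, blocks of 4, total SD 0.138, which gives 80% power by the t distribution) gave 81.5% for Welch and 84.2% with order in the model, a gain of 2.7 points.

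**Hospital.** If hospitals account for an assumed 5%, 10% or 20% of the variance, removing that share lifts power from 80% to about 82%, 84% or 88%. The blocking factor may therefore matter more than order.

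**Bias by hand.** Take 9.5 events per hospital. A failed event has on average (9.5 − 1)/2 = 4.25 events still to come. A replacement put at random among them moves back 1 + 4.25/2 = 3.125 places, or 3.125/8.5 = 0.368 of the sequence. Put at the end, it moves 5.25/8.5 = 0.618. If a share q of copilot events and no control events are replaced, the bias is about −q × shift × L.

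| q, placement | L | by hand | simulated |
|---|---|---|---|
| 15%, random later | 0.03 | −0.15 × 0.368 × 0.03 = −0.002 | about −0.002 |
| 15%, random later | 0.15 | −0.15 × 0.368 × 0.15 = −0.008 | about −0.009 |
| 30%, end | 0.15 | −0.30 × 0.618 × 0.15 = −0.028 | up to −0.030 |

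The hand figures run slightly low because they ignore replacements pushing one another back. With no replacement, or 15% replaced in both arms, simulated bias was about zero. Adding event order to the model brought it to about zero in the uneven settings as well.

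**Type I error of the Welch test.** With 15% against 0% at random later positions it was 4.5% to 5.1% for falls of 0.03 to 0.20. With 30% against 0% at the end it was 9.6% at L = 0.09 and 15% at L = 0.15. The 30% is the extreme in which the whole 15% loss falls on one arm and every lost event is replaced: 0.15 × 76 = 11.4 of 38 events.

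**The case against.** An unadjusted comparison in a randomised trial is valid, and blocking by hospital balances order in expectation. A reader might infer that omitting event order by itself biases the primary result or leaves the trial short of power. The documents support neither. Bias needs a trend and unequal replacement together, and the unadjusted test still has about its planned 80%.

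The evidence for a trend is also thinner than it looks:

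- The Benefits section says "Participation in simulated IHCA events may improve the skills used by both on-site IHCA team members and the telemedical copilot", but the sentence goes on to speak of managing real patients, and the one before it calls direct benefit unlikely. It does not predict falling no-flow fractions.
- It is tempting to say that the same teams repeat. The waiver section puts more than 2000 people in the eligible pool and expects membership to vary. With 1900 participations, that is 1900/2000 = 0.95 or fewer per eligible person on average. Some staff will attend more often, but the extent is not given.
- Study duration mentions "expected intermissions during implementation of a new electronic medical record at some study hospitals". Such gaps would weaken carry-over.

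Nor do the documents say that every failed event is replaced at a fixed late position. Rescheduling is optional, and roll-in make-ups are placed at random. Competing clinical demands are not specific to an arm, and both arms use the telemedicine cart.

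All of this stands, and it limits the point to an inexpensive improvement. What survives is that a replacement cannot precede the event it replaces, so random placement reduces the shift without removing it, and that the plan has nothing to absorb a trend if one exists.

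**Conclusion.** The point holds as a low-cost improvement; the planned analysis is not invalid. For assumed linear falls of 0.03 to 0.15, the forgone gain is about 0 to 3 points of power (just under 4 at the top of the range by the formula alone).

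Bias arises only with a trend and unequal replacement. At 15% against 0% with random later placement, it is about −0.002 to −0.009 in the copilot's favour. The standard error is 0.138 × √(2/38) = 0.032, so this is at most 0.009/0.032 ≈ 0.28 of a standard error, and type I error stays near 5%. It becomes material, up to −0.030 with type I error of 15%, only in the extreme case of 30% against 0% placed at the end with a fall of 0.15.

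These figures rest on assumed alpha 0.05, a back-solved SD, blocks of 4, a linear trend and assumed replacement rates. The documents give neither the size of any trend nor the split of replacements by arm.

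**What to change.** For the primary outcome and the other continuous event-level outcomes, replace the t-test with a prespecified linear model containing:

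- study arm;
- hospital, the blocking factor;
- the event's sequence number within its hospital, counting every mock code started there, including aborted and roll-in events.

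The plan has no linear model to extend, so this changes the primary test and must be written as such. Use heteroscedasticity-robust standard errors to keep the allowance for unequal variances, and name the type. HC2 with a t reference on the residual degrees of freedom suits this sample size; HC3 is more conservative and could give back the power that the covariates gain. Report the number, reason and position of replacements by arm, and keep the Welch test as a sensitivity analysis.

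**Cost.** Only SAP wording changes, since location and date/time are already among the data elements for each event. With 8 hospitals the model uses 7 + 1 = 8 more degrees of freedom, leaving about 74 − 8 = 66. It assumes a common linear trend. If there is neither a trend nor a hospital effect, it loses about 1 point of power or less, absent unequal replacement. It should be fixed before outcomes are seen by arm, because adding it after an imbalance appears would look data-driven.

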Background and Significance: Only 15-30% of patients who suffer in-hospital cardiac arrest (IHCA) survive to hospital discharge.^{1,2} Factors associated with lower mortality and improved function include provision of high-quality, minimally-interrupted chest compressions, prompt administration of epinephrine, and swift defibrillation of eligible arrhythmias.³⁻⁶ Unfortunately, resuscitation teams provide suboptimal care to 25-40% of IHCA victims, with significant variation in IHCA outcomes and process adherence documented between hospitals.^{3,7} Resource limitations and less-experienced providers may explain lower IHCA at small hospitals and on nights and weekends.^{8,9} Although educational and technological interventions may improve patient outcomes, the gap between optimal and actual resuscitation practice remains large.^{1,10} Barriers to effective IHCA resuscitation countered by effective leadership include response teams’ ad hoc formation and variable structure and member expertise.¹¹⁻¹³ Explicit leadership training improves processes of care and outcomes for IHCA resuscitation, but standard Advanced Cardiac Life Support (ACLS) training provides little instruction non-technical skills critical for high-functioning IHCA teams.^{12,14,15} A dedicated, leadership-trained “copilot” on cardiac arrest resuscitation teams may improve IHCA outcomes by performing the same functions — parallel analysis, situational awareness augmentation, action checking, protocol verification, and error correction — for the resuscitation team leader that an airplane copilot provides the pilot during an in-flight emergency. Employing telemedical technology to involve the “copilot” physician will allow this role to be filled by an intensivist physician with particular expertise in care of critical illness and will provide long-term cost and resource efficiencies, particularly in smaller hospitals with fewer available physicians.

Research subjects: We will conduct mock codes at Intermountain Healthcare hospitals, specifically Intermountain Medical Center, LDS Hospital, Riverton Hospital, The Orthopedic Specialty Hospital, McKay-Dee Hospital, Park City Medical Center, and American Fork Hospital.

- Local IHCA team: Intermountain Healthcare employees, resident physicians, and affiliated care providers who are either designated members of each participating hospital’s IHCA response

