teams or act as voluntary responders to announced mock codes will be eligible to participate. The number of on-site participants for each simulated IHCA event is expected to average 15-25.

- Telemedical intensivist IHCA copilot: Board-certified or board-eligible critical care medicine physicians on the staff of the Intermountain Healthcare Telecritical Care Center will act as IHCA team copilot. The total number of expected participants is up to 30.

Recruitment:

- Local IHCA team: IHCA team activation will employ the participating hospital's standard mechanism. A sign posted outside the room used for the mock code will indicate that a video-recorded simulation is taking place. After completion of the simulation, participants will receive an information sheet about the study.
- Telemedical intensivist IHCA copilot: Eligible telemedical intensivists will be invited to participate by email and in person.

Methods/Procedures:

- Study design: Randomized, multicenter, simulation-based clinical trial
- Intervention: Standardized consultation to IHCA team by off-site intensivist via two-way audiovisual link using a mobile telemedicine cart
- Control: Display of silent, pre-recorded, non-interactive videotape of an ICU physician. The on-site participants will be told that an intensive care physician is observing the mock code.
- Randomization: Each event will be randomly assigned to intervention or control using block randomization by hospital.
- Procedures:
 - All event will be randomly pre-assigned to intervention (participation via telemedicine link by a remote critical care physician) or control (prerecorded video of telemedicine physician displayed on mobile telemedicine cart).
 - A research coordinator will arrange a time for mock code with local hospital clinical leadership and Code Blue leadership. The remainder of the IHCA team will not be informed that the announced event is a simulation prior to team activation.
 - The research coordinator and an experienced simulation technician will set up simulation equipment in an unused patient care room on the general medical or surgical ward at the hospital, including video recording device and mobile telemedicine cart.
 - Research coordinator will obtain final confirmation with the on duty clinical leadership that simulation will not interfere with patient care.
 - The hospital's on duty IHCA resuscitation team will then be activated via the hospital's standard mechanism.

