Data Collection: A research coordinator will be present at all mock codes. Besides study implementation duties, the coordinator will record team composition and function, processes of care, and leadership behaviors. Additional data will be obtained from (1) the simulator device, (2) the defibrillator device, (3) review of video recording of simulation event, (4) a brief questionnaire completed by IHCA team members upon completion of the mock code, and (5) a brief questionnaire completed by the telemedical physician copilot.

Data elements for collection

- Telemedical critical care physician (“copilot”)
 - Name
 - DOB
 - Email
 - Telephone
 - Race/ethnicity
 - Year completed medical school
 - Year completed post-graduate training
 - Date of first experience with telecritical care
 - Telecritical care shifts per year
 - Sex
 - Age
 - Credential type (MD vs DO)
 - Experience with in-person cardiac arrest events led
 - Date/time of each study simulation participation
 - Opinions about impact, utility, and feasibility of “copilot” interaction (survey)
 - Opinions about impact, utility, and feasibility of “copilot” interaction (post-participation qualitative interview)
- On-site code team participants
 - Event ID
 - Profession
 - Specialty (if physician)
 - Role on IHCA team
 - IHCA team participation frequency
 - Experience participating in mock code
 - Opinions about code team function during mock code
 - Opinions about impact, utility, and feasibility of “copilot” interaction
 - Short form State-Trait Anxiety Inventory^{16,17}
- Simulation events (see also Table 1)
 - Location
 - Date/time of event
 - Participant numbers and professions
 - Simulation duration
 - Date/time of key response parameters (i.e. team leader arrival)
 - Date/time of key resuscitation events
 - CPR quality
 - Interventions by IHCA team
 - ACLS protocol adherence
 - ACLS protocol deviation & errors

- Etiology identification
- IHCA team function
- Debriefing (Y/N) and themes
- Telemedicine interface function
- Leadership behaviors by IHCA team leader

Privacy, Confidentiality and Data Management

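### The primary t-test ignores hospital, the blocking factor, and night or weekend timing; it stays valid, but adjusting for both could gain precision at little cost

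*Combined protocol and SAP*

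**What the plan says.** All references are to the combined protocol and SAP.

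- **Analysis.** Under Data analysis: "Between-group comparisons for continuous variables will employ two-sided t-tests with unequal variance". The no-flow fraction is continuous and measured once per event, so this is the only method that covers the primary outcome. No adjusted or sensitivity analysis of it is specified. The multilevel models in the same section apply to survey responses and carry a random effect for event, not hospital.
- **Randomisation.** Under Methods/Procedures: "Each event will be randomly assigned to intervention or control using block randomization by hospital". Timing is not a stratification factor.
- **Prognosis.** Under Background and Significance: "Resource limitations and less-experienced providers may explain lower IHCA at small hospitals and on nights and weekends".
- **Scheduling.** Under Procedures: "A research coordinator will arrange a time for mock code with local hospital clinical leadership and Code Blue leadership". The arm is already fixed by then: "All event will be randomly pre-assigned to intervention". No section says how many events, if any, will run at night or on a weekend.
- **Data held.** The simulation-event data elements include location and "Date/time of event".

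**The concern.** When allocation is balanced within hospitals, differences between hospitals largely cancel out of the arm difference. An unadjusted t-test still counts them as error. Its standard error is then larger than the true sampling error, so the confidence interval is too wide and the test rejects less often than its nominal level. The protocol itself gives a reason to expect such differences, since it points to small hospitals.

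Night and weekend timing is the second candidate. It is known before the simulation starts, it is already recorded, and the protocol mentions it in the same sentence. If some events are off-hours and no-flow fraction differs then, that variation also stays in the error term.

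What is at stake is precision in a trial of 76 events sized for 80% power. The choice of covariates also needs to be made in advance: picking them after seeing an imbalance would be data-driven.

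**Working it through.** **1. The plan's own figure.** The plan gives 76 events (38 per arm), 80% power and an absolute difference of 0.09. It states no SD and no alpha, so 76 cannot be reproduced independently. Assuming two-sided alpha 0.05, the SD can be solved for:

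- Normal approximation: SD = 0.09 / [(1.960 + 0.842) × √(2/38)] = 0.140.
- t distribution with 74 df: SD = 0.138, used below. The standard error is 0.138 × √(2/38) = 0.0317.
- If 15% loss leaves about 32 per arm (38 × 0.85 = 32.3), the normal-approximation SD is 0.1285. The relative gains are nearly the same.

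**2. Timing.** Let p be the off-hours share and g the off-hours difference in no-flow fraction. Neither is in the documents; both are assumptions. The variance explained is R² = p(1−p)g²/SD², and the residual SD is SD × √(1−R²).

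| p | g | R² | Power, cost of the covariate ignored | Power, cost counted |
|---|---|---|---|---|
| 0 | any | 0 | 80.0% | indicator not estimable; no gain |
| 0.20 | 0.03 | 0.16 × 0.0009 / 0.0191 = 0.008 | 80.3% | 79.8% |
| 0.25 | 0.06 | 0.1875 × 0.0036 / 0.0191 = 0.035 | 81.4% | 80.9% |
| 0.50 | 0.10 | 0.25 × 0.0100 / 0.0191 = 0.131 | 85.2% | 84.7% |

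The last column averages over 3,000 random draws of the indicator. It allows for its chance correlation with arm and the lost degree of freedom.

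**3. Chance imbalance is not a second harm.** Its SD is g × √(2p(1−p)/38). At p = 0.50 and g = 0.10 this is 0.0115. As a share of the variance of the arm difference, (0.0115/0.0317)² = 0.13, which is the R² already counted in step 2. The t-test's standard error already contains it.

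**4. Hospital.** The share of variance due to hospital, 5-20%, is an assumption. Compared with the nominal 80%:

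- 5%: SD 0.138 × √0.95 = 0.1345; 0.09 / (0.1345 × √(2/38)) = 2.92; power about 82%.
- 20%: SD 0.138 × √0.80 = 0.1234; 0.09 / (0.1234 × √(2/38)) = 3.18; power about 88%.

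I checked this by simulation: eight hospitals with 8-10 events each, arms equal within hospital, equal variances, 40,000 trials per setting.

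| Hospital share | Welch size | Welch power | Adjusted power, HC2 | Adjusted power, HC3 |
|---|---|---|---|---|
| 0% | 5.1% | 80.2% | 80.0% | 76.3% |
| 5% | 4.5% | 80.4% | 81.7% | 78.1% |
| 20% | about 3% | 83.3% | 88.0% | 85.2% |

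Two things follow. Blocking alone already lifts the Welch test's power somewhat when hospitals differ, so the gain over the test as it would really perform is about 1 to 5 points (81.7 − 80.4 = 1.3; 88.0 − 83.3 = 4.7). The +2 to +8 is measured against the planned 80%. The choice of robust estimator also matters: HC2 keeps the gain, while HC3 is conservative in this layout and gives up about 3-4 points.

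**5. Cost if neither factor matters.** The documents give between seven and nine sites (nine on the title listing, seven under Research subjects, 7-8 under Study duration). Hospital therefore uses 6-8 degrees of freedom and timing one, 7-9 in all. Losing nine degrees of freedom alone takes power from 80.0% to 79.9%. Simulated with both factors null and a quarter of events off-hours, power was 79.3% with HC2 against 80.2% for Welch, about 1 point lower.

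**The case against.** The strongest case against is that the Welch test is a valid primary analysis for randomised events and that the timing gain rests on two inputs the documents do not supply. Mock codes are arranged with local leadership and need a simulation technician and an unused room, so nearly all may fall in weekday hours. The indicator would then be close to constant and useless. The Background sentence is hedged and concerns real arrests, not no-flow fraction in simulations. All of this stands, and it is why timing is the conditional half of the point. It does not touch hospital, which is the design's own blocking factor.

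A reader might go further and infer that timing imbalance biases the planned test. The documents do not support that. Chance imbalance neither biases the estimate nor inflates type I error. Systematic imbalance is conceivable: the arm is fixed before the time is arranged, nothing says the scheduler is blind to it, only intervention events need a live intensivist, and aborted events may be rescheduled in the same arm. If the off-hours share differed by an assumed 20 percentage points between arms, the shift would be 0.20 × 0.03 = 0.006 to 0.20 × 0.10 = 0.020. But nothing shows that slots differ by arm, and a single indicator would remove only the part of such an imbalance that it captures.

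**Conclusion.** The point holds as one of efficiency, not validity. The planned test omits the factor on which randomisation is blocked, so if hospitals differ its intervals are too wide and its size falls below 5% (to about 3% at a 20% hospital share). Adjusting for hospital would bring power to about 82-88% against the planned 80%, or 1 to 5 points above what the Welch test would itself achieve under blocking. Adjusting for timing adds between nothing and about 5 points, and nothing if all events are in weekday hours.

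These sizes rest on assumed values: SD 0.138, 38 analysed events per arm, alpha 0.05, a hospital share of 5-20%, an off-hours share of 20-50% and an off-hours difference of 0.03-0.10. It would be wrong to say that precision is certainly lost to timing, or that the planned test gives a biased answer.

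**What to change.** In Data analysis, make the primary analysis a linear model of no-flow fraction on arm and hospital, plus an off-hours indicator.

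- Define off-hours in advance from the recorded date/time (night or weekend versus weekday daytime).
- State a rule, applied without reference to arm, for dropping the indicator when off-hours events are too few. One example is below a tenth of analysed events, where power before any covariate cost is only 80.2-81.5% for g of 0.03-0.09.
- Use small-sample robust standard errors, to keep the tolerance of unequal variances that the Welch test provides. Name the estimator: HC2 preserves the gain here, whereas HC3 is safe but would use up much of it.
- Report the adjusted arm difference with its 95% CI as primary, and the Welch t-test as a sensitivity analysis.
- Tabulate event timing by arm, so that any uneven scheduling can be seen.

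If the team prefers to keep the Welch test as primary, the adjusted model should at least be a pre-specified sensitivity analysis.

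The cost is plan wording, since no new data or design change is needed, plus 7-9 degrees of freedom and about 1 power point if neither factor matters. It should be settled before arm-level results are seen.
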